2. STUDY OBJECTIVES

2.1 Primary objective(s)

The study will include patients with advanced neuroendocrine neoplasms in four different cohorts with the following primary endpoints:

Primary endpoint for cohorts 1, 2 and 3:

Nine-months clinical benefit rate (CBR) by Response Evaluation Criteria In Solid Tumors (RECIST 1.1), which is defined as the percentage of patients achieving complete response (CR), partial response (PR), or stable disease (SD) at month 9 after durvalumab plus tremelimumab was started.

Primary endpoint for cohort 4:

Nine-months overall survival rate, which is defined as the percentage of patients alive at month 9 after durvalumab plus tremelimumab was started.

Clinical Study Protocol
 Drug Substance DURVALUMAB/TREMELIMUMAB
 Study Number ESR 15-11561-61-DUNE
 EudraCT Nº: 2016-002858-20
 Edition Number: 5.0 dated on June 09th, 2021

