4.3 Withdrawal of Subjects from Study Treatment and/or Study

Permanent discontinuation of investigational product/study treatment

An individual subject will not receive any further investigational product if any of the following occur in the subject in question:

1. Withdrawal of consent or lost to follow-up.
2. Adverse event that, in the opinion of the investigator or the sponsor, contraindicates further dosing.
3. Subject is determined to have met one or more of the exclusion criteria for study participation at study entry and continuing investigational therapy might constitute a safety risk.
4. Pregnancy or intent to become pregnant.
5. Any AE that meets criteria for discontinuation as defined in Section 10.3.
6. Grade ≥ 3 infusion reaction.
7. Subject noncompliance that, in the opinion of the investigator or sponsor, warrants withdrawal; eg, refusal to adhere to scheduled visits.
8. Initiation of alternative anticancer therapy including another investigational agent.
9. Confirmed PD by RECIST 1.1 (CT scan or MRI at 4-6 weeks that confirms progression) and investigator determination that the subject is no longer benefiting from treatment with durvalumab + tremelimumab. Patients with documented tumor progression by image (all time-points but especially at 12 weeks), the progression should be confirmed with an additional imaging test (same characteristics) within 4-6 weeks. Treatment should continue according to protocol, until disease progression is confirmed, according the aforementioned procedure.
10. No restarts are allowed after a delay of more than 12 weeks due to toxicity or more than 4 weeks of delay if **the reason is different from toxicity** without consulting the Coordinating Investigator.

Subjects who are permanently discontinued from further receipt of investigational product, regardless of the reason (withdrawal of consent, due to an AE, other), will be identified as having permanently discontinued treatment.

Subjects who are permanently discontinued from receiving investigational product will be followed for safety per Section 10.0 and Appendix 1 or 2, including the collection of any protocol-specified blood specimens, unless consent is withdrawn or the subject is lost to follow-up or enrolled in another clinical study. All subjects will be followed for survival. Subjects who decline to return to the site for evaluations will be offered follow-up by phone every **3 months as an alternative**.

Withdrawal of consent

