9. DISEASE EVALUATION AND METHODS

Primary Objective

Disease evaluation according RECIST 1.1.

A copy of the RECIST 1.1 guideline will be included in the ISF.

RECIST 1.1 will be modified so that PD must be confirmed at the next scheduled visit, preferably, and no earlier than 4 weeks after the initial assessment of PD in the absence of clinically significant deterioration. Treatment with durvalumab + tremelimumab would continue between the initial assessment of progression and confirmation for progression.

Secondary objectives (irRECIST)

The response to immunotherapy may differ from the typical responses observed with cytotoxic chemotherapy including the following (Wolchok et al 2009, Nishino et al 2013):

- Response to immunotherapy may be delayed
- Response to immunotherapy may occur after PD by conventional criteria
- The appearance of new lesions may not represent PD with immunotherapy
- SD while on immunotherapy may be durable and represent clinical benefit.

Based on the above-described unique response to immunotherapy and based on guidelines from regulatory agencies, e.g., European Medicines Agency's "Guideline on the evaluation of anti-cancer medicinal products in man" (EMA/CHMP/205/95/Rev.4) for immune modulating anti-cancer compounds, the study may wish to implement the following in addition to standard RECIST 1.1 criteria:

- RECIST 1.1 will be modified so that PD must be confirmed at the next scheduled visit, preferably, and no earlier than 4 weeks after the initial assessment of PD in the absence of clinically significant deterioration. Treatment with durvalumab + tremelimumab would continue between the initial assessment of progression and confirmation for progression.
- In addition, subjects may continue to receive durvalumab + tremelimumab beyond confirmed PD in the absence of clinically significant deterioration and if investigators consider that subjects continue to receive benefit from treatment.

Progression would be considered confirmed if the following criteria are met:

- ≥20% increase in the sum diameters of target lesions compared with the nadir at 2 consecutive visits with an absolute increase of 5 mm, and/or
- Clinically significant progression (worsening) of non-target lesions or new lesions at the confirmatory PD time point compared with the first time point where progression of non-target lesions or new lesions was identified, and/or

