Data cut-off for the primary study analysis will happen following after the last patient included in the study has performed the first tumor evaluation (week 12 after first dose of study drug). The following tumor evaluations will take place every 12 weeks until documentation of disease progression or start of another anticancer therapy.

Analysis of primary efficacy variable

The analysis of clinical benefit rate and overall survival rate will be performed independently for each study cohort when the last patient included in the corresponding cohort of the study will arrived to 9 months after inclusion in the study or have progressed. The primary objective of the study will be based on the investigator assessment.

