3.7.2 Planned Analyses

Demographic and other baseline characteristics

Demographic and other baseline characteristics will be summarized and listed. For continuous demographic/baseline variables including age, weight, and vital signs, results will be summarized and presented as n, number of not available data (NA), mean, standard deviation, median, and minimum and maximum values. For categorical variables such as race/ethnicity, the number and percentage of subjects will be used.

Prior and concomitant medications

Concomitant medications will be assigned an 11-digit code using the World Health Organization Drug Dictionary (WHO DD) drug codes. Concomitant medications will be further coded to the appropriate Anatomical-Therapeutic-Chemical (ATC) code indicating therapeutic classification. Prior and concomitant medications will be summarized and listed by drug and drug class.

Efficacy Analyses

All efficacy analyses will be based primarily on the Full Analysis Set and secondarily on the Per Protocol Analysis Set.

Data cut-off for the primary study analysis will happen following after the last patient included in the study has performed the first tumor evaluation (week 12 after first dose of study drug). The following tumor evaluations will take place every 12 weeks until documentation of disease progression or start of another anticancer therapy.

Analysis of primary efficacy variable

The analysis of clinical benefit rate and overall survival rate will be performed independently for each study cohort when the last patient included in the corresponding cohort of the study will have arrived to 9 months after inclusion in the study or have progressed. The primary objective of the study will be based on the investigator assessment.

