3.7.6 Interim Analyses

Not applicable

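### The plan gives two timings for the primary analysis without saying which governs, and its 9-month trigger accepts progression as enough to analyse cohort 4 survival

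*Protocol*

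**What the plan says.** Protocol section 11.1, under Efficacy Analyses, sets a study-wide data cut-off for the primary analysis: it follows "after the last patient included in the study has performed the first tumor evaluation (week 12 after first dose of study drug". The next paragraph, headed as the analysis of the primary efficacy variable, covers the clinical benefit rate (CBR) and the overall survival rate. It analyses each cohort separately when that cohort's last patient "will arrived to 9 months after inclusion in the study or have progressed".

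SAP section 3.7.2 carries the same pair: the cut-off after the last patient in the study "has performed the first tumor evaluation (week 12 after first dose of study drug", and the per-cohort analysis when the last patient "will have arrived to 9 months after inclusion in the study or have progressed". SAP sections 2.1 and 2.2 of the efficacy part repeat only the per-cohort rule.

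Protocol section 2.1 measures both primary endpoints at month 9 from the start of treatment. For cohorts 1 to 3 the endpoint is CBR. For cohort 4 it is "the percentage of patients alive at month 9 after durvalumab plus tremelimumab was started". SAP section 3.7.6 on interim analyses reads "Not applicable".

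**The concern.** The two timings differ in unit (whole study or single cohort), in event (week-12 scan or month 9) and in date. A month-9 endpoint cannot be observed at week 12 in recently enrolled patients, and no interim look is planned that would give the week-12 sentence another purpose.

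The 9-month trigger has its own fault. For CBR, progression can settle a patient's outcome as a failure. For cohort 4 it settles nothing, because the endpoint is vital status and Protocol section 8.1.3 follows survival regardless of later treatment. The sentence names the overall survival rate and makes no exception for cohort 4.

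At stake is which data set enters the primary binomial test. An outcome not yet reached at the cut-off would be handled by the multiple imputation in Protocol section 11.2 and SAP sections 3.7.3 and 3.7.5. The missing-at-random assumption in SAP 3.7.5 is stated only for CBR. The rule on loss to follow-up and treatment discontinuation does not address patients who are simply short of month 9.

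**Working it through.** The documents give no figure for this point. The check is date arithmetic on the week-12 sentence taken as the actual cut-off, with one month = 365.25/12 = 30.44 days.

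**Gap**
- Week 12 = 84/30.44 = 2.76 months.
- Gap to month 9 = 9 − 2.76 = 6.24 months.
- Month 9 = 9 × 30.44/7 = week 39.1.

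**Share of patients short of month 9** = fraction entering in the last 6.24 months of accrual. Even accrual is an assumption. The documents support three patterns:
- Protocol 13.6 milestones (half enrolled by December 2017, the rest by December 2019): 0.5 × 6.24/24 = 13.0%.
- Even over the 33 months in Protocol 13.6: 6.24/33 = 18.9%.
- Even over the 24 months in Protocol 3.1 and SAP 3.8.1: 6.24/24 = 26.0%.

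**Counts in a cohort that follows the study's pattern to its last entry**
- Of 31: 4.0, 5.9, 8.1.
- Of 33: 4.3, 6.2, 8.6.
- A cohort whose last patient entered more than 6.24 months before the study's last patient: none.

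These counts are patients short of month 9. Those who already have an event have a settled outcome, so fewer would need imputation. The documents give no accrual by cohort, so the counts are illustrations and not bounds.

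**The trigger set against each endpoint**
- Cohorts 1 to 3: progression means failure, subject to the plan's own confirmation rule. Protocol section 9 says "PD must be confirmed at the next scheduled visit, preferably, and no earlier than 4 weeks after the initial assessment of PD", absent clinically significant deterioration, and section 4.3 says "the progression should be confirmed with an additional imaging test (same characteristics) within 4-6 weeks".
- Cohort 4: a patient who has progressed may be alive or dead at month 9, so the trigger can be met while the endpoint is unknown.
- Clock: the trigger counts from inclusion and the endpoints from start of treatment.

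**Which scan is month 9?** The Protocol schedule of assessments, Protocol 8.1.2 and 11.1, and SAP 3.7.2 scan every 12 weeks. SAP 3.5 and 3.5.1 scan every 8 weeks to week 48. Week 39.1 falls between weeks 36 and 48 on the first schedule and close to week 40 on the second, and no scan is designated.

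**Delay against a week-12 cut-off**
- Cohort 4 at month 9: 6.2 months.
- Cohorts 1 to 3: week 36 gives 8.28 − 2.76 = 5.5 months, week 40 gives 9.20 − 2.76 = 6.4, and week 48 gives 11.04 − 2.76 = 8.3.
- Waiting for a 4 to 6 week confirmation adds 0.9 to 1.4 months.

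**The case against.** The intended rule can largely be worked out. The Protocol says the cut-off happens following the week-12 scan, which can mean no earlier than that scan, and a minimum does not conflict with a later analysis. Such a minimum would have a plausible purpose, because the Per Protocol set requires a week-12 tumor assessment.

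The 9-month rule sits under the specific heading for the primary variable and is the only timing in SAP 2.1. The primary tables are for CBR and survival at 9 months. The report dates also fit: Protocol 13.6 has last entry in December 2019 and the report in December 2022, and SAP 3.8.1 has December 2018 and April 2020, 16 months apart.

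A reader might infer that the primary tests are to be run at week 12 with up to a quarter of patients immature. The text permits that, but the evidence above makes it unlikely. A reader might also infer that one patient's early progression would release a whole cohort's analysis. The words about the last patient allow it literally, but every patient is the more natural meaning.

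This reduces the seriousness but does not remove the point. A sentence called a data cut-off should fix one, and nothing states that it is only a minimum. The cohort 4 fault remains on either reading, although survival is followed after treatment stops, so the data should exist and only the trigger is wrong.

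**Conclusion.** The point holds as a modest fault of specification. Two timings stand side by side with no rule of precedence. The 9-month rule is probably the intended one, but its progression alternative does not fit the cohort 4 endpoint.

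If the week-12 sentence were applied as written, 13% to 26% of patients would be short of month 9, and those without an event would fall to imputation. That range rests on even accrual and on which of the documents' timetables is used. No bias can be quantified: the documents give neither accrual by cohort nor a cohort 4 progression rate.

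On the Protocol 13.6 dates, the week-12 cut-off (about March 2020) and month 9 (about September 2020) both precede Edition 5.0 of June 2021. The practical need may therefore be to put on record the cut-off that was used.

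**What to change.** - In Protocol 11.1 and SAP 3.7.2, delete the week-12 cut-off sentence or state that it is only a minimum.
- In the same sections and in SAP 2.1 and 2.2, state one rule per cohort. Apply it to every patient and time it from first dose, or from allocation for patients never dosed, since the Full Analysis Set is all allocated subjects.
- Cohorts 1 to 3: each patient has had the month-9 tumor assessment, has already failed by the primary endpoint's definition, or has ended tumor follow-up. Say whether the cut-off waits for confirmation of progression first seen on that scan.
- Cohort 4: each patient has vital status known at 9 months, has died, is lost to follow-up or has withdrawn consent. Remove the progression alternative.
- Reconcile the 12-weekly and 8-weekly scan schedules so that the month-9 scan can be identified.
- If the analysis has been run, state the cut-off used.

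The cost is text edits. The analysis comes about 6 months later than a week-12 cut-off, or 8.3 months plus any confirmation time if week 48 were named. With last entry in December 2019, that is about September to December 2020, before the planned last visit of December 2021. No patients or visits are added.

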11.2. Methods of statistical analyses

Strategic decisions about future development of immune therapy in neuroendocrine tumors will be available after the results of this trial.

Summary tables (descriptive statistics and frequency tables) will be provided for all baseline variables, efficacy variables, and safety variables, as appropriate. Continuous variables will be summarized with descriptive statistics (mean, standard deviation, range, and median). Ninety-five (95) percent confidence intervals (95% CI) may also be presented, as appropriate. Frequency counts and percentage of subjects within each category will be provided for categorical data.

The primary efficacy analysis will be performed using the binomial test procedure. Missing data will be treated using statistical multiple random imputation.

Secondary endpoints will be summarized with descriptive statistics. Continuous variables will be summarized with n, mean, standard deviation, and range, frequency counts and percentage of subjects within each category will be provided for categorical data. Multivariate regression models will be used to study relations between explanatory variables and primary endpoint. Survival analysis will be performed to analyze PFS, Kaplan-Meier curves will be presented and possible comparisons will be tested using the log-rank test or the Cox proportional hazard model for multivariate analysis, hazard ratios (HR) and their 95% confidence interval (CI95%) will be provided. Patients with lost of follow-up or treatment discontinuation will be included in the final analysis of primary endpoint if they have at least one tumor evaluation and considered as censored data for survival endpoints.

R software version 3.2.1 will be used for all analysis.

Safety Analyses

Safety analyses will be based on the Safety Analysis Set. All safety analyses will be summarized separately by cohort. Adverse events and serious adverse events, laboratory test results, physical examination findings and vital signs, and their changes from baseline will be summarized using descriptive statistics. Abnormal values will be flagged.

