Secondary endpoints will be summarized with descriptive statistics. Continuous variables will be summarized with n, mean, standard deviation, and range, frequency counts and percentage of subjects within each category will be provided for categorical data. Multivariate regression models will be used to study relations between explanatory variables and primary endpoint. Survival analysis will be performed to analyze PFS, Kaplan-Meier curves will be presented and possible comparisons will be tested using the log-rank test or the Cox proportional hazard model for multivariate analysis, hazard ratios (HR) and their 95% confidence interval (CI95%) will be provided. Patients with lost of follow-up or treatment discontinuation will be included in the final analysis of primary endpoint if they have at least one tumor evaluation and considered as censored data for survival endpoints.

R software version 3.2.1 will be used for all analysis.

Sample Size Determination:

Sample size has been calculated using one-sample Superiority test (function One Sample Proportion. (NIS) of the Trial Size package of R software). According to previous knowledge, it is estimated that the reference value for the likelihood to be progression-free at 9 months is 30% and we expect an increase of 20% with a superiority margin of 10%. With a unilateral alpha level of 5% and 80% power, we estimate to include 28 patients per group, with an expected lost to follow-up rate of 10%, a final sample size in each 1, 2 and 3 cohort will include 31 patients.

For cohort 4, and according to previous knowledge, it is estimated that the reference proportion of patients being alive at 9 months is 13% and we expect an increase of 10% with a superiority margin of 5%. With a unilateral alpha level of 5% and 80% power, we estimate to include 30 patients per group, with an expected lost to follow-up rate of 10%, a final sample size will include 33 patients.

Summarizing, total sample size will include 126 patients: 31 patients for cohorts 1 to 3, and 33 for cohort 4.

Clinical Study Protocol
Drug Substance DURVALUMAB/TREMELIMUMAB
Study Number ESR 15-11561-61-DUNE
EudraCT Nº: 2016-002858-20
Edition Number: 5.0 dated on June 09th, 2021

Clinical Study Protocol
 Drug Substance DURVALUMAB/TREMELIMUMAB
 Study Number ESR 15-11561-61-DUNE
 EudraCT N°: 2016-002858-20
 Edition Number: 5.0 dated on June 09th, 2021

SCHEDULE OF STUDY ASSESSMENTS (according to section 8)

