6.1.2 Procedures for handling subjects incorrectly enrolled

Patients incorrectly enrolled in the trial will be considered as protocol deviations. If investigator considerer that the patient is obtaining benefit of the investigational treatment, patients could continue on therapy. They will not be considered for the primary endpoint of the trial, neither for efficacy nor biomarker secondary and exploratory analyses. Patients incorrectly enrolled that continue on treatment can be assessed for safety profile endpoint.

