11. STATISTICAL METHODS AND SAMPLE SIZE DETERMINATION

11.1. Description of analysis sets

The statistical analyses described in this section will be performed as further outlined in the Statistical Analysis Plan, which will be included in the clinical study report for this protocol.

Analysis Sets

The analysis sets will be defined as follows:

- **Full Analysis Set** will include all allocated subjects. This will be primary analysis set for the efficacy endpoints.
- **Per Protocol Analysis Set** will include those subjects who were allocated and received at least one dose of the assigned study drug and had no major protocol deviations. The subjects will complete both baseline and at least one post-baseline tumor assessments (week 12).
- **Safety Analysis Set** will include all subjects who were allocated and received at least one dose of the study drug and had at least one post-baseline safety evaluation (week 12). This will be the analysis set for all safety evaluations.
- **Pharmacodynamic Analysis Set**: All the subjects who have received at least one dose of study drug and have evaluable pharmacodynamic data.

Demographic and other baseline characteristics

Demographic and other baseline characteristics will be summarized and listed. For continuous demographic/baseline variables including age, weight, and vital signs, results will be summarized and presented as n, number of not available data (NA), mean, standard deviation, median, and minimum and maximum values. For categorical variables such as race/ethnicity, the number and percentage of subjects will be used.

Prior and concomitant medications

Concomitant medications will be assigned an 11-digit code using the World Health Organization Drug Dictionary (WHO DD) drug codes. Concomitant medications will be further coded to the appropriate Anatomical-Therapeutic-Chemical (ATC) code indicating therapeutic classification. Prior and concomitant medications will be summarized and listed by drug and drug class.

Efficacy Analyses

All efficacy analyses will be based primarily on the Full Analysis Set and secondarily on the Per

Clinical Study Protocol
 Drug Substance DURVALUMAB/TREMELIMUMAB
 Study Number ESR 15-11561-61-DUNE
 EudraCT Nº: 2016-002858-20
 Edition Number: 5.0 dated on June 09th, 2021

Protocol Analysis Set.

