3.7.5 Missing Data

Assuming that the pattern of missingness in the primary endpoint variable (clinical benefit rate at 9 months) are missing at random (1), missing data will be treated using statistical multiple random imputation (2,3,4). Once data are collected, according to the missing data pattern observed, it should be considered if pre-specified methods are appropriate. A full reporting of all reasons for patient discontinuation should be given where possible, in order to identify the most important reasons that caused it. As suggested by the EMA (2), the seed of the pseudorandom number generator that will be used to randomly generate imputations for the missing values is pre-specified ("55881234") to avoid bias being introduced by *post hoc* selection of the seed and therefore the random numbers to be imputed.

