2 EFFICACY ANALYSES

All efficacy analyses will be based primarily on the Full Analysis Set and secondarily on the Per Protocol Analysis Set.

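### A tumour-evaluation condition on the primary analysis conflicts with the all-allocated Full Analysis Set, and leaving out patients without a scan can raise month-9 clinical benefit in cohorts 1-3

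*Protocol*

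**What the plan says.** Four rules bear on who is counted in the primary analysis.

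- **Scan condition.** Protocol 11.2, the synopsis (Statistical Methods and Data Analysis) and SAP 3.7.3 carry the same sentence on patients lost or off treatment: "lost of follow-up or treatment discontinuation will be included in the final analysis of primary endpoint if they have at least one tumor evaluation". It goes on to treat these patients as censored for survival endpoints.
- **Analysis set.** Under Protocol 11.1 and SAP 3.7.1 the Full Analysis Set "will include all allocated subjects. This will be primary analysis set for the efficacy endpoints". SAP section 2 (Efficacy Analyses) repeats: "All efficacy analyses will be based primarily on the Full Analysis Set and secondarily on the Per Protocol Analysis Set". A post-baseline scan is required only for the Per Protocol set: "The subjects will complete both baseline and at least one post-baseline tumor assessments (week 12").
- **Missing data.** Protocol 11.2 and SAP 3.7.3: "Missing data will be treated using statistical multiple random imputation". SAP 3.7.5 assumes that "missingness in the primary endpoint variable (clinical benefit rate at 9 months) are missing at random". SAP 3.7.8 bases percentages on the non-missing sample size.
- **Incorrectly enrolled patients.** Protocol 6.1.2 and SAP 3.3.4: "They will not be considered for the primary endpoint of the trial". SAP Table 3 (section 1.1.2) also describes the Full Analysis Set more narrowly, as patients who meet all eligibility criteria.

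In the SAP 2.1.1 table for CBR, the only negative row names progressive disease alone.

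**The concern.** An allocated patient who is lost or stops treatment without a post-baseline scan could be left out (scan condition), multiply imputed (missing-data rule), dropped from the percentage base (SAP 3.7.8) or kept in the denominator (Full Analysis Set). No passage says which rule governs.

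The choice is unlikely to be neutral. Protocol 11.1 and SAP 3.7.2 place the first tumour evaluation at week 12, so these patients have gone before then, and early departure in advanced disease often means progression, death or toxicity. Each cohort is a single arm judged against a fixed reference, so no control arm offsets an upward shift. With 31 patients per cohort, two or three can change the outcome.

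The survival part of the sentence raises a separate problem, for PFS and OS. Protocol 3.3, 4.3 and 8.1.3 require survival follow-up after treatment stops, and Protocol 3.3 and Appendix 2 require scans to continue. Censoring because treatment stopped would discard those data, and such censoring may be informative.

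**Working it through.** **Inputs.** Protocol 11.3 gives, for cohorts 1-3, a reference rate of 30%, one-sided alpha of 5%, 28 patients, 10% expected loss and a final 31. Protocol 11.2 gives a binomial test. Assumed, because the documents do not give them: the share *f* of patients without a scan, and the month-9 benefit rate *b* among those patients. The null is taken as 30%; the plan does not say whether the 10-point margin is added to it.

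**The plan's own step.** 28 × 1.1 = 30.8, which gives 31 (28/0.9 = 31.1). So the plan expects about three patients lost per cohort.

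**Cut-offs** (smallest count with exact one-sided p ≤ 0.05 against 30%): 15 of 31, 14 of 30, 14 of 29, 13 of 28. With all 31 analysed the exact size is 2.4%, below 5% because the test is discrete.

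**Effect of leaving patients out.** If the true rate over all allocated patients is 0.30, the rate among those kept is (0.30 − *f·b*)/(1 − *f*). Type I error = Σ over *m* of Bin(*m*; 31, *f*) × P[Bin(31 − *m*, rate among those kept) ≥ cut-off for 31 − *m*].

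| Share without scan | Rate among those kept if *b*=0 | Error, *b*=0 | Error, *b*=15% | Error, *b*=30% (random) |
|---|---|---|---|---|
| 0% | 30.0% | 2.4% | 2.4% | 2.4% |
| 2% | 30.6% | 3.6% | 3.3% | 3.1% |
| 3% | 30.9% | 4.2% | 3.7% | 3.2% |
| 5% | 31.6% | 5.2% | 4.3% | 3.5% |
| 10% | 33.3% | 8.1% | 5.6% | 3.7% |

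The last column rises slightly although nothing is biased, because smaller samples have cut-offs that use more of the 5%. If the tested null and true rate are 40%, the *b*=0 errors are 3.2% with nobody omitted, 6.5% at a 5% share and 9.7% at 10%.

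**At the boundary, with three patients omitted.**

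| Patients with benefit | Three left out | All 31 kept |
|---|---|---|
| 13 | 13/28 = 46.4%, p = 0.049 | 13/31 = 41.9%, p = 0.107 |
| 14 | 14/28 = 50.0%, p = 0.021 | 14/31 = 45.2%, p = 0.053 |

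**The case against.** The sentence says if, not only if, and does not say that the tumour evaluation must be post-baseline. Every patient has a screening scan, so on a literal reading almost nobody is excluded. The rules could also be read together: all allocated patients in the denominator, observed data where a scan exists, imputation otherwise. Neither answer settles it. Protocol 11.1 calls the week-12 scan the first tumour evaluation, the condition has no purpose if baseline scans satisfy it, and nothing says that imputation covers patients without a scan.

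The objection on size is stronger and largely stands. Scans continue after treatment stops, and Protocol 8.1.3 implies a disease assessment at end of treatment unless one was done in the previous 28 days. The group without any post-baseline scan may therefore be small. A reader might take the 10% in Protocol 11.3 as its size, but that figure is overall loss to follow-up, with no time limit.

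A reader might also infer that imputation would certainly inflate the result. The documents name no imputation model or pooling rule, so no firm figure can be given. The bias arises if early losses do worse than the model predicts; under the assumed missing at random it need not arise.

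The SAP has partial safeguards. Section 3.7.5 asks for discontinuation reasons and a second look at the method once the missing-data pattern is known, Table 4 lists excluded patients, and section 3.7.8 annotates tables with missing observations. These show what happened but do not fix the denominator.

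**Conclusion.** The plan is wrong as written: the scan condition conflicts with the all-allocated primary set and is not reconciled with imputation or with percentages on non-missing data. This should be fixed.

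The size is modest and conditional. With 2-3% of patients omitted, type I error stays under 5% even if all are failures. It exceeds 5% at a share of about 5% if all are failures, or about 10% if their benefit rate is 15%. These figures assume a 30% null, N=31, an exact binomial test and omission of patients without a scan.

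The documents do not show that any cohort's result is inflated; they leave open a choice that can decide a result near the cut-off. For cohort 4, a reader might infer that the 9-month survival rate is equally affected. That follows only if the scan or imputation rule is applied to vital status. SAP 3.7.5 names CBR alone, although the general wording in Protocol 11.2 and SAP 3.7.3 has no cohort limit.

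The survival clause is a defect in its own right, but it gives no censoring date, so its effect on PFS and OS cannot be sized.

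**What to change.** - Delete the scan condition from the synopsis, Protocol 11.2 and SAP 3.7.3, and keep all allocated patients in the primary denominator. Align SAP 3.7.5 and 3.7.8 with this.
- If incorrectly enrolled patients stay excluded (Protocol 6.1.2, SAP 3.3.4, SAP Table 3), write the exception into the Full Analysis Set definition, on baseline eligibility only.
- Cohorts 1-3: count patients with no post-baseline tumour evaluation, and deaths before month 9, as not having CBR. Relabel the negative row in the SAP CBR tables to include them. Classify an isolated missed month-9 scan from adjacent scans, using the confirmed-progression rule in Protocol section 9.
- Report multiple imputation and the evaluable-only result as sensitivity analyses.
- Cohort 4: use vital status at 9 months, regardless of scans or treatment status.
- Do not censor PFS or OS only because treatment stopped.
- Also show the result under the present wording. The protocol edition is dated June 2021 and Protocol 13.6 planned the last enrolment for December 2019, so the change is late.

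The cost is wording only, since the scans and survival follow-up are already required. CBR becomes slightly conservative, and power falls if missing scans are common. As an illustration, if 10% of patients lack a scan but would have had the same benefit rate, a true 50% reads as 0.9 × 50% = 45%, and exact power at N=31 (cut-off 15) falls from 64% to 42%.
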